Study Protocol

Personalized Feedback After Alcohol Health Education for Members of Greek Life (GREEK Study)

NCT05107284

July 7, 2022

Principal Investigator:

[name].

Description and Purpose of the Project

Heavy episodic alcohol use within the college student population is widespread, creating problems for student drinkers, their peers, and their institutions. Negative consequences from heavy alcohol use can be mild (e.g., hangovers, missed classes), to severe (e.g., assault, even death). Although online interventions targeting college student drinking reduce alcohol consumption and associated problems, they are not as effective as in-person interventions. Online interventions are cost-effective, offer privacy, reduce stigma, and may reach individuals who would otherwise not receive treatment. In a recently completed randomized, controlled trial, an emailed booster with personalized feedback improved the efficacy of a popular online intervention (Braitman & Henson, 2016). A second randomized, controlled trial confirmed efficacy for students of legal drinking age for a longer timeline (Braitman & Lau-Barraco, 2018). Although promising, the booster incorporated in the study needs further empirical refinement.

Primary Aims

The current project seeks to build on past progress by further developing and refining the booster. In particular, the current project is an extension of previous work by expanding the investigation into complete social networks (students involved in Greek life). This booster contains feedback about alcohol use tailored to the recipient, and will be emailed 2, 6, 10, and 14 weeks after baseline (experimental condition), or not at all (control condition). This study will be conducted specifically with students who are members of fraternities or sororities (specifically, those in the organizations that agree to participate). This population engages in heavy alcohol use, so is ideal for an alcohol intervention. Members of fraternities and sororities (i.e., "Greek life") engage in more frequent drinking, consume more when drinking, and have higher peak drinking occasions than students not involved in Greek life. We aim to administer the intervention and associated booster among complete networks of Greek organizations to examine how the intervention and booster progress through social networks. Moreover, given the close connections among members of fraternities and sororities, these may be closed peer networks that could facilitate the examination of how changes in drinking occur through social influence. In other words, we can potentially examine if change happens through selection (i.e., transitioning into friendships with individuals who are similar), such that those who drink less after the intervention change who they drink with to those individuals in the organization who also drink less; or socialization (i.e., becoming more similar to individuals who one spends time with), or drinking less through peer influence because participants may drink less to match the individuals they drink with, who are drinking less after the intervention and booster.

Thus, the current study has two primary aims (to be examined regardless of study outcomes or participation rates) and an exploratory, secondary aim (to be examined only if the booster is efficacious and the majority of members for each organization enrolled complete the study). Primary Aim 1: We will examine the efficacy of a personalized feedback booster emailed after eCHECKUP TO GO for Alcohol among members of fraternities and sororities. We expect initial post-intervention drinking reductions for both study conditions, with individuals in the booster condition reporting further reductions at later follow-ups. Primary Aim 2: Given the focus on perceived descriptive norms and protective behavioral strategies in the personalized

feedback boosters, we will examine if the booster impacts changes in those constructs over time. We expect individuals in the booster condition will report further reductions in norms and increases in protective behavioral strategies at later follow-ups. Exploratory, Secondary Aim: If the emailed booster is efficacious and the majority of members for each organization enrolled complete the study, we will examine social mechanisms of change (i.e., through selection versus socialization).

Participant population

Eligible participants must 1) be 18 years of age or older, 2) be an undergraduate student at a participating institution; and 3) be a member of a participating fraternity or sorority. Power analyses were conducted using Monte Carlo simulation methods within Mplus (version 5.21, Muthén & Muthén, 2002). Effect sizes, variance, and covariances used were based on data from a preliminary study with a similar protocol (some participants receiving the intervention only, others receiving the intervention plus booster) among college drinkers (Braitman & Henson, 2016; Braitman & Lau-Barraco, 2018). We estimated a retention rate of 76%, the average reported in a meta-analysis of RCTs assessing alcohol interventions for first-year college students (Scott-Sheldon et al., 2014). Monte Carlo simulation methods indicated that for the effect size expected ($b = 6.57$, $\beta = 0.537$) and for the expected 24% attrition, a sample size of $N = 180$ total students should yield sufficient power (.80+) to detect booster effects.

Recruitment Procedure

An email is sent to presidents of fraternities and sororities at the participating institutions. We explain the purpose and design of the study, share relevant approvals (IRB, NIH Certificate of Confidentiality, etc.), and explain the benefits of participation, including monetary compensation. Presidents who opt in for their chapter's participation share membership lists (names and email addresses). Names on membership lists are used for social network assessment in each survey (described in more detail in the Measures section below). Research staff then send recruitment emails to all members in participating organizations. This email contains similar content as the email sent to chapter presidents (i.e., study purpose and design, relevant approvals, compensation structure). We also ask chapter presidents if we may attend a chapter meeting to describe the study in more detail and answer questions. Some but not all organizations have chosen to do this so far. Undergraduate research assistants who are also members of Greek life make these visits. Recruitment emails include a link to Calendly to schedule their participation for the baseline session via Zoom.

Study Procedure

Members of Greek life are recruited via email as described above. Participants schedule their participation time through an online time management system (Calendly). They receive an email reminder from the Calendly system 24 hours before their assigned timeslot. After participating in the fully remote baseline session via Zoom, participants are to be paid \$20. Participants are invited to complete additional 1-, 3-, and 6-month assessments, and receive \$5 for each completed follow-up survey. As an additional incentive, participants who complete all assessments will be given a \$5 bonus (yielding a \$40 total for the study if all follow-ups are completed). All monetary compensation is provided via online gift card to Amazon.

Baseline: Participants sign on to Zoom via the link provided during their assigned timeslot. Upon signing into the Zoom meeting, the research assistants provide a link (using the chat function) directing them to a Qualtrics survey. Participants read and view videos of the study procedures on the first page of this website. The videos have been created in Powtoon, using voiceover and images that are not related to a specific gender or race/ethnicity. After reviewing the videos, participants are provided with the informed consent document (on a subsequent page of the survey), and will have the opportunity to ask questions during the live Zoom session with the research assistant. After consenting to participate, they are directed to complete the baseline survey (approximately 30-45 minutes). All participants will complete this computerized survey that assesses alcohol use, alcohol-related problems, protective behavioral strategies for drinking and their perceived effectiveness, alcohol-related cognitions (motives, expectancies, and beliefs about alcohol use), social network characteristics, cannabis and tobacco use, COVID-19 pandemic experiences, internalizing symptoms, and demographic measures. After completing the initial assessment, participants are then be directed to navigate through the eCHECKUP TO GO program (San Diego State University Research Foundation, 2018) until it is completed (approximately 20-30 minutes).

Subsequent assessments: Approximately 1, 3, and 9 months after the initial assessment, researchers send each participant an email reminding them to complete the follow-up assessment. This email includes a link to an online follow-up survey that assesses alcohol use, related problems, protective behavioral strategies for drinking and their perceived effectiveness, social network characteristics, and cannabis and tobacco use. If participants provide additional ways to contact them during the baseline survey (a second email address, a phone number to text), these methods are also used to send the link to the follow-up surveys.

Boosters: After the intervention, participants receive additional emails from the researcher, depending on their study condition. For the intervention-plus-booster study condition, these emails contain personalized normative feedback about alcohol use as well as feedback about harm reduction strategies, serving as a booster to the original intervention. Baseline data are used to provide students with normative information (e.g., typical drinking among ODU students who are male/female), and reminders of protective behavioral strategies they can use to reduce drinking-related harm (separated by strategies they have reported using recently versus those they might consider trying). This is received at 2 weeks, 6 weeks, 10 weeks, and 14 weeks after baseline. Participants in the intervention-only control condition do not receive any feedback via email. Participants are assigned to study condition at the group level, so that an entire organization receives the booster emails (or the entire organization does not).

Measures

The same measures are included in baseline and the follow-up surveys:

Participants' **alcohol use** is assessed using a modified version of the Daily Drinking Questionnaire for the past 30 days (Collins et al., 1985). Additionally, participants describe specific aspects regarding their drinking in the past 30 days (e.g., highest consumption in a single day). **Descriptive Norms** are assessed by modifying the DDQ to reflect their expectations for typical male students at the same institution, typical female students at the same institution, and

close friends. **Injunctive Norms** are assessed using 10 items (Carey et al., 2010). **Alcohol-related problems** are assessed using the 24-item Brief Young Adult Alcohol Consequences Questionnaire (BYAACQ; Kahler et al., 2005). **Protective behavioral strategy** (PBS) use is assessed using the Protective Drinking Practices Scale (PDPS; Martin et al., 2020). **Alcohol expectancies** are assessed using the Comprehensive Effects of Alcohol questionnaire (CEOA; Fromme et al., 1993). **Motives for alcohol use** are assessed using the Drinking Motives Questionnaire (DMQ; Cooper, 1994). **Alcohol beliefs** about how salient alcohol use is to college life are assessed using the College Life Alcohol Salience Scale (CLASS; Osberg et al., 2010). **Social network** and affiliated characteristics are assessed using the adapted version (DeMartini et al., 2013) of the Brief Important People Interview (BIPPI; Zywiak et al., 2002). They are asked to list the top 5 people they consider their closest friends in their organization, and are presented with dropdown menus to list other members of their organization. There are also two write-in boxes to list individuals outside of their organization they consider a very close friend. **Cannabis use** is assessed using recommended best practices (Prince, 2019), and **tobacco use** is assessed using items created by the researcher. **Perceived Importance of Marijuana to the College Experience Scale** (PIMCES; Pearson et al., 2017) is used to assess how salient marijuana/cannabis is to college life. Questions about participants' experiences with the COVID-19 pandemic were created by the researchers. **Symptoms of depression** are assessed using the short version of the Center for Epidemiological Studies Depression scale (CESD-10; Andresen et al., 1994), altered to reflect the past 30 days. **Anxiety** is assessed using the Generalized Anxiety Disorder 7 (GAD-7; Spitzer et al., 2006), modified to reflect the past 30 days. **Stress** is assessed using the psychological vulnerability subscale of the Perceived Stress Scale – Revised (PSS-R; Wickrama et al., 2013), modified to reflect the past 30 days. **COVID-19-specific stress** is assessed using the COVID-19 Stress measure (Ellis et al., 2020). **Demographics and general information** are assessed during the initial assessment only. Participants report their age, race, sex, GPA, class standing, military affiliation, first generation college student status, athletic status, residential status, relationship status, sexual identity, height, and weight (for blood alcohol content calculations).

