## **Statistical Analysis Plan**

Prior to hypothesis testing, the data will be examined for normality and outliers. Histograms and values for skewness and kurtosis will be examined. Positively skewed variables will be natural log transformed, unless paired with an excessive number of zeroes. If there are an excess of zeroes in an outcome, the variable will be dichotomized if other values are not well represented, or appropriate modeling techniques will be used (e.g., hurdle models) if other values are well represented. Boxplots will be used to check for outliers. Extreme values will be winsorized (i.e., cases retained in the sample, but values made less extreme). Cases with missing data will be compared to complete cases across major study variables to identify if there are systematic differences in missingness. If significant associations are identified, these variables will be used as covariates in later analyses.

To address Primary Aim 1 of the study, the data will be analyzed using latent growth models within a structural equation modeling framework. Separate models will be conducted for each alcohol outcome: alcohol consumption (e.g., quantity), and alcohol-related problems. It is not known the exact trajectory across time (baseline, 1 month, 3 months, 6 months), so a few models will be compared to identify which best captures the shape of change over time. A simple model that reflects change to 1 month (slope 1; initial change post-intervention) and longer-term maintenance (slope 2; linear growth to 9 months) will be compared to models with additional curvilinear components in case longer-term maintenance is not a linear process. Study condition will be dummy coded with “no booster” as the category of reference, and will serve as a predictor of each latent variable (latent intercept, each slope). All models will be conducted using maximum likelihood estimation, and will control for sex. The model for problems will also control for alcohol quantity.

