Given that the tailored feedback boosters address both descriptive drinking norms and protective behavioral strategies, these are considered secondary outcomes. Models identical to the one described above will be conducted (e.g., latent growth models with two slopes, regressed on study condition), but with norms and protective behavioral strategies serving as the outcomes of interest rather than alcohol use or related problems (addressing Primary Aim 2). Given prior findings that emailed booster feedback containing personalized normative feedback and protective behavioral strategies (PBS) was significantly more effective for select groups (i.e., those lower in PBS use [Braitman & Henson, 2016], legal age drinkers [Braitman & Lau-Barraco, 2018]), we will examine potential moderators of booster efficacy as a supplementary exploratory analysis. Legal drinking status by age (coded as 1 = *age 21-24* [legal], 0 = *age 18-20* [underage]) and baseline PBS use (in its original continuous metric) will be explored as potential moderators. The moderator and its interaction with study condition will be added as predictors of each latent factor (latent intercept, slope 1, and slope 2). All models will be conducted in Mplus (version 8; Muthén & Muthén, 1998–2019) using maximum likelihood estimation.

For the Exploratory, Secondary Aim, RSIENA will be used to conduct stochastic, actor-based models (Ripley et al., 2017). These will allow us to examine if behavior change precedes network changes (i.e., selection), or if network changes precede behavior change (i.e., socialization). These models will only be conducted if reductions in drinking or related problems are evidenced in the Primary Aim 1 examination (i.e., there is behavior change over time), and if several members of each organization participate (so network change can be examined over time).

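### The .80+ power claim at N = 180 students gives no cluster-level input, although whole organizations are assigned to condition

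*Protocol*

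**What the plan says.** **Power.** Under Participant population, the protocol reports a Monte Carlo simulation in Mplus with b = 6.57, beta = 0.537 and 24% attrition. It concludes that 180 "total students should yield sufficient power (.80+) to detect booster effects". The effect sizes, variances and covariances come from preliminary work described at participant level: "some participants receiving the intervention only, others receiving the intervention plus booster". The paragraph gives no organization count, members per organization, ICC or design effect.

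**Assignment.** Under Study Procedure, the Boosters paragraph states: "Participants are assigned to study condition at the group level, so that an entire organization receives the booster emails". The organization is thus the unit of assignment.

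**Within-organization dependence.** Under Primary Aims, the protocol says "We aim to administer the intervention and associated booster among complete networks of Greek organizations". One route to change that it considers is "drinking less through peer influence because participants may drink less to match the individuals they drink with".

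**Analysis.** The SAP regresses the latent intercept and each slope on study condition. It adds: "All models will be conducted using maximum likelihood estimation, and will control for sex". For norms and protective strategies (Primary Aim 2), "Models identical to the one described above will be conducted". The SAP text available for this review names no organization-level term and no cluster-robust standard error. Part of the SAP was not available.

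**The concern.** When whole organizations are assigned, the information about a condition effect depends on how many organizations there are and how alike their members are, as well as on the number of students. The power statement counts only students. The protocol does not say that its simulation ignored clustering. That is inferred from the missing inputs and from the participant-level description of the source data. A zero ICC cannot be taken for granted, because members influencing one another's drinking is one of the mechanisms the study hopes to examine.

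Two outcomes are possible, and a reader cannot tell which applies:

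- If the growth models are run without an organization term, the test of condition rejects a true null more often than 5% under any positive ICC. A booster effect could then be claimed falsely. The same error would carry into Aim 2 and into the exploratory network aim, which the protocol makes conditional on efficacy.
- If an organization-aware test is used, power may lie above or below .80. If it lies well below, a null result could be misread as evidence against the booster.

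**Working it through.** **Inputs from the protocol.** N = 180, retention 76%, beta = 0.537.

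**Assumptions, because the documents are silent.** Two-sided alpha 0.05; equal arms; K organizations of equal size; ICC from 0 to 0.10; beta read as a standardized mean difference (d). The simulation itself cannot be repeated, because the growth-model variances, covariances and target parameter are not given. A comparison of two means stands in for it.

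**Step 1: the stated figure with independent students.** Completers: 180 × 0.76 = 136.8. Noncentrality: 0.537 × √136.8 / 2 = 3.140. Normal-approximation power is .88, or .95 if all 180 contribute. Either is compatible with .80+.

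**Step 2: add organizations.** Design effect: DEFF = 1 + (n/K − 1) × ICC. Noncentrality: 3.140/√DEFF for completers. If all 180 contribute through maximum likelihood, it is 3.602/√DEFF. Power is from the noncentral t with K − 2 degrees of freedom. N = 180 means 30, 15 or 9 students per organization at K = 6, 12 or 20.

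Worked case, completers, K = 6, ICC 0.05: DEFF = 1 + (22.8 − 1) × 0.05 = 2.09; noncentrality 3.140/√2.09 = 2.17; 4 df; power .38.

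| Power at d = 0.537 | K = 6 | K = 12 | K = 20 |
|---|---|---|---|
| Completers, ICC 0 | .66 | .81 | .84 |
| Completers, ICC 0.01 | .58 | .77 | .82 |
| Completers, ICC 0.05 | .38 | .63 | .74 |
| All 180, ICC 0.01 | .67 | .86 | .91 |
| All 180, ICC 0.05 | .42 | .70 | .82 |

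The ICC 0 row shows the loss from degrees of freedom alone.

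**Step 3: largest ICC at which power is still .80.**

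- Completers: none at K = 10 or fewer (.785 at K = 10 even with ICC 0); 0.002 at K = 12; 0.011 at 16; 0.021 at 20.
- All 180: none at K = 6; 0.016 at 10; 0.024 at 12; 0.060 at 20.

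**Step 4: minimum detectable d at .80 power, completers, K = 6, 12, 20.** At ICC 0.01: .71, .56, .52. At ICC 0.05: .93, .66, .58.

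**Step 5: the other reading of beta.** If beta is standardized on both variables, d = 2 × 0.537 / √(1 − 0.537²) = 1.27. Completer power at ICC 0.05 is then .96 or more with 6 or more organizations, but .66 with 4.

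**Step 6: type I error without an organization term.** 2 × (1 − Φ(1.96/√DEFF)). This does not depend on beta.

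| Type I error, completers | K = 6 | K = 12 | K = 20 |
|---|---|---|---|
| ICC 0.01 | .08 | .06 | .06 |
| ICC 0.05 | .18 | .11 | .09 |

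**Check by simulation** (20,000 runs per cell; 132 to 140 students; K = 6, 12, 20). A t-test on organization means had power .58, .76, .83 at ICC 0.01 and .39, .62, .75 at 0.05. Across the simulated settings its type I error was .047 to .052. A student-level t-test at ICC 0.05 had type I error .176, .106, .087.

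**The case against.** The strongest reply is that nothing is shown to be miscalculated. The .80+ agrees with the student-level proxy, the simulation may have held a cluster component that the text does not describe, and on the fully standardized reading of beta the claim survives with 6 or more organizations even at ICC 0.05. All of this stands, and it is why the conclusion is that the figure is unsupported, not that power is below .80. The favourable reading still needs an adequate number of organizations, which is not stated, and it does nothing for type I error.

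A second reply is that much of the shortfall comes from the choice of test. A large-sample z reference at ICC 0.01 gives .81, .85 and .86 for K = 6, 12 and 20, against .58, .77 and .82 with K − 2 degrees of freedom. This is true, but a z reference is liberal with few organizations and so does not rescue the design.

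A third is that the false-positive risk belongs to the analysis model and not to the power sentence. Under the model without an organization term, the rejection rate at d = 0.537 and ICC 0.05 is .79, .83 and .85 for K = 6, 12 and 20, so .80+ roughly holds for that test. But that test has a type I error of .09 to .18, so its rejection rate is not usable power. It is also right that restating power alone would not cure the analysis; the fix has to name the test as well.

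**Conclusion.** The concern holds. The .80+ figure is unsupported for a trial that assigns whole organizations, and the available SAP text does not say which test it refers to. This is a gap in justification, not an arithmetic slip, and power below .80 is not proven.

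With d = 0.537, power over the tabulated settings with ICC above zero runs from .38 to .91. With d = 1.27, it is .96 or more at ICC 0.05 and 6 or more organizations. If organization is left out of the model, completer type I error is about .06 to .08 at ICC 0.01 and .09 to .18 at 0.05.

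Confidence is high that the inputs are missing, and lower for any particular power value. The figures rest on a two-mean proxy for a growth-model effect and on the assumptions listed above. The relevant ICC is that of change after adjustment for sex, which the documents do not give. The 136.8 and 180 figures bracket the number of students contributing in the proxy; they do not bound the power of the actual growth model. This should be corrected because it bears on the primary efficacy claim.

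**What to change.** - Re-run the simulation with students nested in the actual or planned number of organizations, over a stated ICC range (for example 0.01 to 0.10), using an organization-aware test with a small-sample correction.
- Replace the .80+ sentence with the resulting power, or the minimum detectable effect, at N = 180. State the organization count, members per organization, ICC range, alpha, sidedness, allocation, target growth factor and how beta is standardized. If the existing simulation already included clustering, report these inputs from it.
- Name the same test in the SAP for the Aim 1 models. Aim 2 then inherits it, since its models are defined by reference to Aim 1. Fixing it before results are seen prevents a data-driven choice.

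The cost is one nested simulation, one restated protocol passage and one added SAP line. The downside is a probably less favourable stated power and wider intervals. The change restates what N = 180 can support; it does not ask for more enrolment.
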